## 3. Study design

### 3.1 Design overview

The proposed open label study is single-center randomized, phase II clinical trial designed to address the following specific aims:

- a) **To optimize an MR protocol to characterize the range and rates of *baseline and dynamic* measures of metabolism and energy homeostasis following an acute IV fructose challenge.** Volumetric and quantitative measures of hepatic lipid deposition, energy levels, and water homeostasis will be characterized in normal volunteers to determine typical ranges and coefficients of variation for each technique.
- b) **To differentiate the baseline and dynamic changes of metabolic and energy homeostasis following an acute IV fructose challenge in patients with biopsy-proven NAFLD.** MR-based measurements from the Aim 1 protocol will be correlated to clinical measures of metabolism, energy homeostasis and histologic disease activity before, during and at 4 and 24 hours following IV fructose challenge in regions co-localized and distant from biopsy.

A cohort study of healthy volunteers (n=30) and patients with NAFLD (n=70) will be enrolled. Healthy volunteers will have no evidence of chronic liver disease (normal liver enzymes and normal liver imaging and/or a liver biopsy performed for clinical evaluation of liver disease but whose pathology results note no pathologic abnormalities). Patients with suspected NAFLD who will undergo a standard-of-care liver biopsy, or who have had a historical biopsy within 6

months of the Screening visit, will have both acute intravenous fructose challenge for assessing baseline and post-dietary intervention *static and dynamic* measures of metabolism and energy homeostasis. Co-localization of liver biopsy with MRI to optimize / assess MRI measures of the histologic features of NAFLD will be performed to develop MRI as a surrogate “biomarker” for liver biopsy. With the exception of the liver biopsy, no accurate non-invasive biomarker for disease activity currently exists.

Screening for eligibility and collection of baseline data will span up to 8 weeks. Patients who have had a liver biopsy showing NAFLD within 6 months of the Screening visit or patients who will be undergoing a standard of care percutaneous liver biopsy for NAFLD will be consented.

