## 5. Intravenous Fructose Challenge with MRS Measures of Energy Homeostasis

IV fructose challenge with MRS measures of energy homeostasis will be performed in the morning after an overnight fast. For all subjects, a vein will be catheterized and a venous blood sample drawn for laboratory evaluation (uric acid, glucose, insulin, lipids, and free fatty acids). A slow infusion of isotonic sodium chloride solution will be started to maintain catheter patency. After baseline MR data sets are obtained, fructose (250 mg/kg of body weight) dissolved in 25 to 50 mL of isotonic sodium chloride solution will be infused rapidly (over 30-60 seconds) through the indwelling venous catheter; further spectra will be collected for 1 hour. The slow saline infusion will be continued until the end of the study. At that time, another venous blood sample will be collected for laboratory evaluation (uric acid, glucose, insulin, lipids, and free fatty acids).

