- Unstable therapy for components of the metabolic syndrome (ie. recent starting or stopping of insulin sensitizing agent, lipid lowering agent, and/or antioxidant therapy). Recent starting or stopping (for more than 7 days) the use of a thiazolidinedione (pioglitazone or rosiglitazone) 90 days before the entry biopsy or anytime thereafter
- Use of any prescription or over-the-counter medication or herbal remedy that are believed to improve or treat NASH or liver disease or obesity for the 90 days prior to baseline liver biopsy or prior to randomization
  - Patients must not take any other agent to treat NASH except the treatment assigned after randomization.
- Inability to safely obtain a liver biopsy
- Active substance abuse including inhaled or injection drugs in the year prior to screening
- Pregnancy, planned pregnancy, potential for pregnancy and unwillingness to use effective birth control during the trial, breast feeding
- Any other condition which, in the opinion of the investigator, would impede compliance or hinder completion of the study
- A contraindication to MRI examinations
- Extreme claustrophobia
- Weight or girth exceeds the scanner capabilities
- Any condition or circumstance that, in the opinion of the site investigator, would interfere with completion of MR examinations
- Failure to give informed consent

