## 9. Trial protocol—Study Visits and Events

### 9.1. Visit schedule overview

***Healthy controls*** will ONLY undergo:

- Screening for eligibility for enrollment (1-2 visits over a maximum of 8 weeks)
- Acute intravenous fructose challenge with measure of metabolism and energy homeostasis by magnetic resonance spectroscopy (MRS) (baseline and assessment of change over 60 minutes).
- MRI of the liver

Data collected from healthy controls will be used as reference and optimization values for which study will assess metabolic and energy homeostatic measures in those with NAFLD.

***Patients with NAFLD*** will undergo the following related activities study phases:

- Screening for eligibility for enrollment (1-2 visits over a maximum of 8 weeks)
- Acute intravenous fructose challenge with measure of metabolism and energy homeostasis by magnetic resonance spectroscopy (MRS) (baseline and assessment of change over 60 minutes. MRI of the liver

- Co-localization of non-invasive MR biomarkers with liver biopsy procedure.

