## 9.2. Screening and Baseline Data Collection

Patients who appear to be eligible after chart review and have completed of standard of care tests and procedures for NAFLD or suspected NAFLD will be invited to undergo screening. Recording of screening data may not start until the patient has signed the consent statement. Screening and baseline data collection procedures will include questionnaires, physical examination, measurement of fasting serum glucose and insulin, routine liver, lipid and metabolic tests, uric acid and urine analysis for pregnancy testing. Standard therapy for NAFLD will be reviewed. Risks, potential benefits and alternatives to study participation will be reviewed in detail.

Patients suspected of having NAFLD, requiring a standard of care biopsy to establish their diagnosis and guide their clinical management, will be approached to participate in this study. Patients with a historical biopsy confirming NAFLD within 6 months of the Screening visit will also be approached to participate in this study.

All participants who sign the consent statement will be registered in the trial database. Patient charts will be reviewed for historical information. Each participant who starts screening will be accounted for at the end of screening, as either screening success (enrolling in the trial) or a screening failure. A screening failure is defined as a participant who signed the consent form, but is found to be ineligible prior to randomization; patients who meet medical eligibility criteria but who refuse enrollment in the trial; and patients whose liver biopsies do not meet entry criteria. Reasons for screening failure will be recorded in the trial database.

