The patient will sign the consent at screening visit to obtain any tests and procedures needed to finalize eligibility after chart review and will undergo a history and physical examination to identify other abnormalities and contraindications for participation. Anthropomorphic assessments (body weight [kg], body height [m], body mass index [BMI], waist circumference [cm], hip circumference [cm] and waist-to-hip ratio; vital signs (systolic and diastolic blood pressure, heart rate, respiratory rate, body temperature); and general physical findings, including hepatosplenomegaly, peripheral manifestations of liver disease, ascites, wasting or fetor, will be collected and recorded. Use of anti-NASH, antidiabetic, statin and fibrate medications in the 90 days prior to the biopsy will be obtained and recorded. Laboratory test results that need to be recorded from chart review or obtained as part of screening visit 1 include hepatitis B (HBsAg) and hepatitis C (anti-HCV), antinuclear antibody (ANA), anti-smooth muscle antibody (ASMA), anti-mitochondrial antibody (AMA), ceruloplasmin (if patient is less than 40 years old), A1AT concentration, iron and transferrin saturation, immunoglobulins (IgA, IgG, IGM), fasting glucose, insulin, and free fatty acids; CBC (Hgb, WBC, platelets, MCV, hematocrit), prothrombin time and INR, complete metabolic panel (sodium, potassium, chloride, bicarbonate, calcium, phosphate, BUN, creatinine, uric acid, albumin, total protein), GGT and hepatic panel (ALT, AST, alkaline phosphatase, total bilirubin, direct bilirubin), fasting lipid profile (total cholesterol, triglyceride, LDL, HDL), and hemoglobin A1c (HbA1c). Frequency and amount of alcohol intake will be obtained. Women of childbearing potential must have a negative pregnancy test.

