## 9.3. Visit Day -1

All patients will be provided with a “standard” meal the day prior to the fructose challenge MRI in order to control for dietary composition and calorie intake prior to intravenous fructose challenge. Patients will be NPO after midnight for morning IV fructose MR biomarker measures.

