#### 9.4. Visit Day 0:

Patients with suspected NAFLD, who have not had a biopsy in the prior 6 months, will have a standard of care liver biopsy followed by co-localization of liver biopsy with MR.

Patients will be escorted to the Department of Radiology for baseline MRI/MRS imaging (MRI study protocol and data acquisition sequences detailed in [Appendix A](#)). Time 0 uric acid, insulin, glucose, lipid panel, and free fatty acids will be obtained. IV Fructose will be administered via heplock and dynamic measures of hepatic ATP and other metabolite measures will be obtained over 1 hour. At that time, another venous blood sample will be collected for laboratory evaluation (uric acid, glucose, insulin, lipids, and free fatty acids).

After acquisition of these late hepatic recover ATP measures, for the patients who have not had a historical biopsy in the 6 months prior to screening, a percutaneous liver biopsy will be performed as standard of care. After standard of care procedures and recovery are completed for the percutaneous liver biopsy, a very limited MRI will be performed to co-localize the site of liver biopsy with the exact site of MRI for modeling of non-invasive MRI biomarkers to features of chronic liver disease as characterized on liver biopsy. Subjects with suspected NAFLD may have two MRI's (one for IV fructose challenge and one for co-localization with liver biopsy site). For subjects with NAFLD, study participation will end after completion of the second MRI.

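### The pregnancy test has no stated maximum interval before the IV fructose bolus, and none is listed on Day 0

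*Combined protocol and SAP*

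**What the plan says.** Section 8.3 excludes "Pregnancy, planned pregnancy, potential for pregnancy and unwillingness to use effective birth control during the trial, breast feeding". Verification comes in section 9.2, headed as covering both screening and baseline data collection. Its procedures include "routine liver, lipid and metabolic tests, uric acid and urine analysis for pregnancy testing", and it later adds "Women of childbearing potential must have a negative pregnancy test". Neither statement gives a window before the infusion.

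Two places set the length of this phase. Section 3.1 says "Screening for eligibility and collection of baseline data will span up to 8 weeks". Section 9.1 gives the same limit to both groups for screening alone: "Screening for eligibility for enrollment (1-2 visits over a maximum of 8 weeks").

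The exposure is described in section 5: "fructose (250 mg/kg of body weight) dissolved in 25 to 50 mL of isotonic sodium chloride solution will be infused rapidly", over 30 to 60 seconds, for all subjects.

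**The concern.** An exclusion meant to prevent an exposure should be checked close to that exposure, particularly when the status can change within weeks. Here the check and the exposure are in different parts of the schedule, and no rule links them. If a woman conceives after her test, or was tested too early for a pregnancy to show, nothing in the written Day 0 procedure would detect it before the bolus.

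The protocol sets time limits for other eligibility items. In section 8.3, HbA1c is tied to 60 days before enrollment and the use of NASH medication to 90 days before biopsy or randomization. In section 8.2, a historical biopsy must fall within 6 months of screening. The pregnancy test has no such limit.

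What is at stake is participant safety and faithful application of the protocol's own exclusion. The group comparison and the endpoints are not affected.

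**Working it through.** The plan gives no figure to reproduce, so the check sets the relevant sections side by side.

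**Where a test appears**

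| Place | Content before the infusion | Pregnancy test? |
|---|---|---|
| 9.2 Screening and baseline | Urine test; negative result required | Yes, undated |
| 9.3 Day -1 | Standard meal, then "Patients will be NPO after midnight for morning IV fructose MR biomarker measures" | None listed |
| 9.4 Day 0 | "Patients will be escorted to the Department of Radiology for baseline MRI/MRS imaging"; blood for glucose, insulin, free fatty acids, lipids and uric acid | None listed |
| 5 Challenge procedure | Catheter, the same metabolic blood tests, baseline MR data | None listed |
| Appendix A, MR Slot 1 | Proton and phosphorus baseline acquisitions, then injection | None listed |

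**How old the result could be**

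- The stated window is 8 weeks: 8 × 7 = 56 days.
- Section 3.1 puts baseline data collection inside that window, and section 9.4 calls the Day 0 imaging baseline. If Day 0 therefore falls inside the window, the interval from test to infusion is anywhere from 0 to 56 days.
- Section 9.1 applies the 8 weeks to screening only, and no section limits the time from the end of screening to Day 0. On that reading the interval has no stated maximum.
- On either reading, a result several weeks old complies with the text. So does a test done on the day.

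**Who is affected**

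Both groups. Section 9.1 lists the fructose challenge for healthy controls as well as for patients with NAFLD, and Appendix A puts the healthy volunteers through MR Slot 1, which contains the injection.

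**Whether the risk can be sized**

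An expected count would be n × [1 − (1 − a)^(g/365)], where n is the number of women of childbearing potential, a the annual conception rate despite contraception, and g the interval in days. The documents give none of the three. To show how far the answer depends on assumed inputs, take n = 40 and a = 10%, neither of which comes from the protocol:

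- g = 56: 40 × (1 − 0.9^(56/365)) = 0.64
- g = 90: 40 × (1 − 0.9^(90/365)) = 1.03

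With n = 10, a = 1% and g = 7 the result is 10 × (1 − 0.99^(7/365)) = 0.002. These figures count all conceptions in the interval, including any that a woman would know of by Day 0. The spread reflects the assumptions and tells us nothing specific about this trial, so no figure is carried forward.

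**The case against.** The strongest reply is that the protocol already has layers of protection. Pregnancy and planned pregnancy are exclusions, contraception is required for the duration of the trial, and a negative test is mandatory. A known pregnancy would stop dosing under section 8.3. This stands, and it limits the point to pregnancies that nobody has noticed.

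Second, the test need not be old. The heading of section 9.2 includes baseline, the sentence requiring a negative result stands apart from the laboratory list tied to the first screening visit, and section 9.4 uses baseline for the Day 0 imaging. This also stands. A reader might infer that the test is fixed at the start of screening, so that a 56-day gap is built in. The documents do not say so; they leave the timing open.

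Third, no harm is shown. Section 11.2.1 lists acute metabolic effects of fructose, notes its past recommendation in parenteral nutrition, and does not discuss pregnancy. A reader might infer a documented fetal hazard, and the documents give no support for one. The case rests on the sponsor's own decision to exclude pregnant women and on the low cost of checking.

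Fourth, a Day 0 urine test shares the main weakness of the screening test: it can miss a very early pregnancy. That is correct and limits the benefit.

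None of this supplies the missing link between test and infusion. Local practice may already include a test on the day, but the protocol does not require one.

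**Conclusion.** The gap is real and minor. Pregnancy is an exclusion, its only listed check has no stated maximum interval before the bolus, and a compliant site may, though need not, infuse on a result that is weeks old. This rests on the text alone: testing appears only in section 9.2, and sections 5, 9.3 and 9.4 and Appendix A list none.

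The residual risk is an unnoticed pregnancy despite required contraception. It is probably small, but that is a judgement; the documents do not allow it to be quantified. A reader might wish to attach a probability, or to say that less than one case is expected. Neither is supported, because the number of women, the conception rate and the interval are all unstated and, on one reading, the interval is uncapped. The point is a cheap safety improvement with no bearing on the validity of the analysis.

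**What to change.** Add one sentence to section 9.4: women of childbearing potential, in the healthy-control and the NAFLD groups alike, must have a negative urine pregnancy test on Day 0 before the fructose infusion, and a positive result means no infusion. Both groups should be named because section 9.4 is written mainly around patients with suspected NAFLD. Keep the screening test and the contraception requirement as they are.

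The cost is one urine test per eligible woman at a visit that already includes sampling before the infusion. With 30 + 70 = 100 planned participants, that is at most 100 tests, and fewer in practice because not all participants will be women of childbearing potential. The other downside is a rare late screen failure, which is what the exclusion is meant to produce. The change narrows the gap but does not remove it, since a very early pregnancy may still go undetected. Endpoints, comparisons and analysis stay the same.

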## 9.3. Visit Day -1

All patients will be provided with a “standard” meal the day prior to the fructose challenge MRI in order to control for dietary composition and calorie intake prior to intravenous fructose challenge. Patients will be NPO after midnight for morning IV fructose MR biomarker measures.

#### 9.4. Visit Day 0:

Patients with suspected NAFLD, who have not had a biopsy in the prior 6 months, will have a standard of care liver biopsy followed by co-localization of liver biopsy with MR.

Patients will be escorted to the Department of Radiology for baseline MRI/MRS imaging (MRI study protocol and data acquisition sequences detailed in [Appendix A](#)). Time 0 uric acid, insulin, glucose, lipid panel, and free fatty acids will be obtained. IV Fructose will be administered via heplock and dynamic measures of hepatic ATP and other metabolite measures will be obtained over 1 hour. At that time, another venous blood sample will be collected for laboratory evaluation (uric acid, glucose, insulin, lipids, and free fatty acids).

After acquisition of these late hepatic recover ATP measures, for the patients who have not had a historical biopsy in the 6 months prior to screening, a percutaneous liver biopsy will be performed as standard of care. After standard of care procedures and recovery are completed for the percutaneous liver biopsy, a very limited MRI will be performed to co-localize the site of liver biopsy with the exact site of MRI for modeling of non-invasive MRI biomarkers to features of chronic liver disease as characterized on liver biopsy. Subjects with suspected NAFLD may have two MRI's (one for IV fructose challenge and one for co-localization with liver biopsy site). For subjects with NAFLD, study participation will end after completion of the second MRI.

#### 9.5 Adverse event reporting and Data Safety Monitoring

The investigators and staff will monitor and report adverse events to ensure patient safety. Any unanticipated or adverse events will be reported to IRB and NIH (Sponsor) in compliance with government regulations of event reporting in research studies. [name] [name], Chief of the Division of Gastroenterology and researcher with prior experience in the conduct of IV fructose challenge and MRS will serve as a data-safety monitor if any adverse events arise in the context of this study.

##### 9.5.1. Definitions

**Adverse event:** An adverse event is any untoward medical occurrence that may present itself during treatment or administration with a pharmaceutical product or clinical procedure and which may or may not have a causal relationship with the treatment. Adverse events include any unanticipated problems involving risks to participants, or breaches of protocol which might entail risk to participants. The term "unanticipated problem" includes both new risks and increased rates of anticipated problems.

**Serious adverse event:** A serious adverse event (SAE) is an adverse event occurring at any time during the study that results in death, life-threatening adverse drug experience, inpatient hospitalization or prolongation of existing hospitalization, a persistent or significant disability/incapacity, or a congenital anomaly/birth defect. Other events may also be considered an SAE if, based on medical judgment, the event jeopardized the patient to the point of requiring medical or surgical intervention to prevent the occurrence of any of the conditions for an SAE listed above.

**Unexpected adverse event:** An unexpected adverse event is any adverse event with specificity or severity that is not consistent with the risk information in the study protocol, current investigator brochure, or current package insert.

**Adverse Events associated with the use of the intervention (i.e. fructose administration or restriction):** Any unexpected adverse event for which there is reasonable possibility that the adverse experience may have been caused by the administration of intravenous fructose and/or restriction of dietary fructose.

### 9.5.2. Monitoring for adverse events

Adverse events will be recorded on study data forms whether or not they are thought to be associated with the study. Adverse events may be discovered during regularly scheduled visits or through unscheduled patient contacts between visits. Summary data on adverse events will be promptly assessed by investigators if they occur. Analyses or listings of adverse events will not be provided to the IRBs; however, adverse events involving unanticipated problems involving risks to participants, or breaches of protocol which might entail risk to participants will be reported to the IRB as soon as possible after they are discovered.

## 10. Statistical design and analysis

Coefficients of variance (CV) will be used to evaluate reproducibility of MRS/MRI baseline measures. Intra-class correlations (ICC) will be used to measure absolute test-retest baseline measure reliability for the test-retest subjects. ICCs will be calculated with a model that separates subject, voxel, measurement and error variances using an analysis of variance (ANOVA) method. We will include a number of multi-factorial random effects models (66, 67) which use a restricted maximum likelihood (REML) algorithm to prevent negative variance terms. The ANOVA model for metabolite estimates across all subjects will be  $M_{ijk} = \mu + S_i + V_{ij} + N_k + e_{ijk}$  where  $\mu$  is the average across all voxels,  $S_i$  = subject,  $V_{ij}$  = voxel and  $N_k$  = scan random effects, respectively and  $e_{ijk}$  is residual error. For ICC in individual subjects, we leave out the  $S_i$  term. ICCs for test-retest measures will be based on random-effects analysis of the variance models and will be computed as follows:  $ICC = \sigma^2_B / (\sigma^2_B + \sigma^2_w + \sigma^2_e)$  where  $\sigma^2_B$  is generalized between-subject variance of metabolites,  $\sigma^2_w$  is within-subject variance between scans 1 and 2 and  $\sigma^2_e$  is variance due to random noise (68). CVs for test-retest reproducibility will be calculated using  $CV = \sqrt{\sigma^2_w + \sigma^2_e} / \mu$ . Similarly we will obtain CVs from the first 20 subjects in Aim2 and will compare these to the normal population.

Dynamic changes will be characterized in a more *ad hoc* manner. From the metabolite estimates at time  $t$  ( $M_{ijkt}$ ), the following parameters will be measured for each individual (subscript  $i$ ): baseline ( $B_i$  = mean of  $M_{jkt}$ , where  $t$  = prior to fructose challenge), range of change from baseline ( $D_i = B_i - \min(M_{jkt})$  if any), time to maximal change ( $T_i$  = time to reach  $\min(M_{ijkt})$ ), time to baseline recovery ( $R_i$ , if applicable). A 95% confidence interval of baseline will be used to test if the metabolite level is recovered to the baseline. If it does not reach the baseline, we will estimate the baseline based on the assumption of a linear recovery rate. Since metabolite levels will be measured at discrete time points, spline smoothing will be used to fit the curve. These values will be averaged across the cohort of volunteers and simple measures of variance calculated.

**10.1 Sample size and Statistical Power Consideration:** Assuming 20% change in hepatic ATP and uric acid (i.e. before~ Normal( $1.2, \sigma^2$ ) and after ~ Normal( $1, \sigma^2$ )), one-side test with alpha = 0.15, the power would be i) if  $\sigma^2 = 1$ , power = 0.523 ii) if  $\sigma^2 = 0.8$ , power = 0.629, iii) if  $\sigma^2 = 0.6$ , power = 0.784, iv) if  $\sigma^2 = 0.5$ , power = 0.875.

**10.2 Analytical and Statistical Approach:** We will test if the acute fructose challenge alters hepatic ATP in healthy volunteers compared to those with NAFLD and whether changes MR parameters and/or energy homeostasis can predict the histologic severity of NAFLD.

**10.3 Management of Missing data:** The occurrence of missing data in this trial is expected to be low. We estimate that careful selection of patients during the screening phase and the consent process should result in no more than 10% missing data from patients who drop out before completing the study.

**10.4 Justification of sample size:** A total of 67 patients will be included to compare the efficacy of acute fructose challenge on the metabolic and energy homeostasis changes in patients with NAFLD.

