### 3.2 Population

Participants at least 18 years of age, both healthy controls and those with suspected NAFLD.

**3.4 Sample size:** 30 healthy controls and 70 subjects with biopsy-proven NAFLD

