## Appendix A:

### **MRI/MRS Protocols for Assessment of Energy Homeostasis and MR Biomarkers for NAFLD**

In all cases no patient repositioning will need to occur between data acquisitions for different MR nuclei. Primary measures are indicated in blue and include  $^1\text{H}$  MRI/MRS for water and fat measures and  $^{31}\text{P}$  UTE MRS for fructose measures. In all cases, the multiple acquisitions acquired prior to the injection of fructose will serve as test-retest cases for confirming measurement variance in the presence of pathology. Interleaved measures for experimental hypotheses may be moved or removed in order to ensure sufficient primary measures within the allotted MR time slot.

Only MR Slot 1 and Slot 2 protocols shown below will be used on the healthy volunteers for Aim 1 in order to optimize these protocols. The full MR protocol shown below will be performed for NAFLD subjects.

MR Slot 1 (Time 0)	MR Slot 2 (Post biopsy)
<math>^1\text{H}</math> MRI - anatomical $^1\text{H}$ MRI/MRS – water/fat $^{31}\text{P}$ UTE MRS – fructose baseline (multiple acquire) Fructose injection $^{31}\text{P}$ UTE MRS – fructose dynamic (multiple acquire) $^1\text{H}$ EPSI – water/fat $^{31}\text{P}$ UTE MRS – fructose dynamic (multiple acquire)	<math>^1\text{H}</math> MRI - anatomical for biopsy localization $^{31}\text{P}$ UTE MRS – fructose recovery (multiple acquire) $^1\text{H}$ MRI/MRS – water/fat

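### Section 10 takes the NAFLD measurement CV from the first 20 patients, while Appendix A plans repeat 31P baselines in all NAFLD patients for the same purpose

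*Combined protocol and SAP*

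**What the plan says.** Section 10 defines the test-retest CV as the square root of the within-subject between-scan variance plus the noise variance, divided by the mean. For patients it then says: "Similarly we will obtain CVs from the first 20 subjects in Aim2 and will compare these to the normal population". This is the only sentence in Section 10 that names a NAFLD sample for the CV, and it gives no reason for the number 20.

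Appendix A describes a wider use of the repeat baselines: "In all cases, the multiple acquisitions acquired prior to the injection of fructose will serve as test-retest cases", and it gives their purpose as "for confirming measurement variance in the presence of pathology". It adds: "The full MR protocol shown below will be performed for NAFLD subjects". In its scan table, the only acquisition before injection that is marked as repeated is 31P UTE MRS. The number of repeats is not given.

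On numbers, Section 3.4 plans "30 healthy controls and 70 subjects with biopsy-proven NAFLD", and Section 3.1 agrees. Section 10.4 instead says "A total of 67 patients will be included".

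**The concern.** The repeat 31P baselines are planned in every NAFLD patient and are designated as test-retest data, yet the operative analysis sentence draws the patient CV from 20 of them. If that sentence is followed as written, the data of 50 of the 70 patients do not enter the estimate.

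What is at stake is how precisely the study can say whether 31P measurement error is larger in NAFLD livers than in healthy ones. This matters beyond the CV itself. Section 10 uses a 95% confidence interval of the baseline to judge whether a metabolite has recovered, and hepatic ATP is the measure named in the principal objectives. A difference in measurement error between the groups would therefore bear on how recovery times are read.

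**Working it through.** The documents state no precision, confidence interval or sample-size reasoning for the CV, so there is no figure of the plan's own to reproduce.

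**Inputs from the documents**
- Patients named for the NAFLD CV: 20 (Section 10).
- NAFLD patients enrolled: 70 (Sections 3.1, 3.4 and 8.1), or 67 (Section 10.4).
- Healthy volunteers: 30 (Section 3.1). This is an upper bound, because the number of test-retest subjects is not stated.
- Missing data: at most 10% (Section 10.3), so about 0.9 × 70 = 63 evaluable.

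**Assumptions**
- Number of repeats per subject, m: 2, 3 or 5, equal in all subjects and both groups.
- Target for power: a 1.5-fold ratio of within-subject SDs, two-sided 5%. This is illustrative.

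**1. NAFLD CV alone.** Degrees of freedom are df = n(m − 1), and the relative SE of a within-subject SD is about 1/√(2 df).

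| m | n = 20 | n = 70 |
|---|---|---|
| 2 | 1/√40 = 15.8% | 1/√140 = 8.5% |
| 3 | 1/√80 = 11.2% | 1/√280 = 6.0% |
| 5 | 1/√160 = 7.9% | 1/√560 = 4.2% |

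The ratio is √(70/20) = 1.87 for every m, because m cancels. With 67 patients it is √(67/20) = 1.83, and with 63 it is √(63/20) = 1.77. Adding the uncertainty of the mean (assumed between-subject CV 10–40%, within-subject CV 5–30%) leaves 1.87 unchanged.

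Chi-square 95% limits at m = 2, as multiples of the estimate, are 0.77 to 1.44 with 20 patients and 0.86 to 1.20 with 70.

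**2. Comparison with 30 healthy volunteers.** SE(log ratio) = √(1/(2 df₁) + 1/(2 df₂)).
- m = 2, 20 patients: √(1/40 + 1/60) = 0.204.
- m = 2, 70 patients: √(1/140 + 1/60) = 0.154.
- Ratio: √[(1/20 + 1/30)/(1/70 + 1/30)] = 1.32, again for any equal m. With 67 patients it is 1.31.

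F-based 95% limits at m = 2, as multiples of the observed ratio, are 0.68 to 1.53 with 20 patients and 0.72 to 1.33 with 70.

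**3. Power for a 1.5-fold SD ratio.** This is a two-sided 5% F test with df₁ = n(m − 1) and df₂ = 30(m − 1), for a true variance ratio of 1.5² = 2.25.

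| m | 20 patients | 70 patients |
|---|---|---|
| 2 | 0.51 | 0.71 |
| 3 | 0.80 | 0.96 |
| 5 | 0.98 | >0.99 |

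At m = 2, power is 0.71 with 67 patients and 0.70 with 63, so neither the disputed total nor the allowance for missing data changes the picture.

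**The case against.** The strongest reply is that the plan never confines the CV to 20 patients. Section 10 says that CVs will be obtained from the first 20, not that later data are excluded, and Appendix A assigns every patient's repeats to the same question. Read together, the two could mean an early check on 20 followed by confirmation in all. This stands in part. A reader might infer that the plan discards the data of the other 50 patients, and the documents do not settle that. But Section 10 is where the analysis is specified and it names 20, so the conflict remains until the text is changed.

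Other limits also stand:
- A reader might carry the near-doubling of the standard error over to the comparison with healthy volunteers. It does not carry over: the 30 volunteers limit precision there, and the factor is 1.32.
- The power gain depends on the unstated number of repeats. With five each, 20 patients are already enough for a 1.5-fold ratio, although the estimate would still be less precise.
- Repeats before injection are documented for 31P only. Section 10 covers MRS and MRI baseline measures generally, and the 1H water/fat acquisition is not marked as repeated.
- The CV formula refers to two scans that the plan does not define, and repeats within one session may not be those scans. Appendix A does, however, designate the pre-injection repeats as test-retest cases.

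Two further inferences lack support. One is that the first 20 patients are scanned while the team is least experienced: Aim 1 optimises the protocol in volunteers, and no learning curve is described. The other is that the CV comparison decides whether the MR measure can be used in patients: no CV threshold or go/no-go rule is stated.

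**Conclusion.** The point holds as a conflict between Section 10 and Appendix A, with a real but modest cost in precision if Section 10 is followed literally. The factors of 1.87 (NAFLD CV alone) and 1.32 (ratio to healthy) rest on an equal number of repeats per subject; the second also assumes that all 30 volunteers contribute repeats. The power figures rest in addition on the assumed number of repeats and on the illustrative 1.5-fold target, and should be read as a range. The conclusion is documented for 31P and should not be extended to 1H water/fat. The primary outcome concerns dynamic changes after fructose and does not depend on this choice. It is a worthwhile improvement, not a threat to the study's main result.

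**What to change.** Change the sentence in Section 10 so that NAFLD CVs and ICCs are estimated from every NAFLD patient with repeat pre-fructose acquisitions, and so that the comparison with the healthy group is reported as a CV ratio with a confidence interval. Keep the first 20 patients only as an early quality check, labelled as such.

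In the same edit, state the number of baseline repeats, say whether they are the two scans in the CV formula, name the measures that have repeats (Appendix A documents 31P), and settle whether the NAFLD total is 70 or 67.

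For 31P this needs no new patients, visits or scans beyond those in Appendix A. The cost is a short text change and a little more analysis work.
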